A Randomized Controlled Trial of Ambient Artificial Intelligence Scribe Technologies
NCT06792890
2025-01-28

Protocol Paper incl. Statistical Analysis Plan

Title: A Randomized Controlled Trial of Two Ambient Artificial Intelligence Scribe
Technologies to Improve Documentation Efficiency and Reduce Physician Burnout

[name]*^Φ

Department of Pediatrics, Division of Immunology, Allergy and Rheumatology and Health
Department of Information Services and Solutions, University of California, Los Angeles

[name], BA^Φ

Division of General Internal Medicine and Health Services Research, David Geffen School
of Medicine, University of California, Los Angeles

[name], MS

Health Department of Information Services and Solutions, University of California, Los
Angeles

[name], MBA, MS

Department of Pediatrics and Office of Health Informatics and Analytics, University of
California, Los Angeles, California, United States

[name] MSHS

Division of General Internal Medicine and Health Services Research, David Geffen School
of Medicine, University of California, Los Angeles and VA Greater Los Angeles Healthcare
System/Geriatrics Research Education and Clinical Center, Los Angeles, California

[name] [name]

Department of Radiation Oncology, David Geffen School of Medicine, University of
California, Los Angeles

[name], MS

Department of Medicine Statistics Core, David Geffen School of Medicine, University of
California, Los Angeles

[name], MPH

Division of General Internal Medicine and Health Services Research, David Geffen School
of Medicine, University of California, Los Angeles

*Corresponding Author: [contact]

^Φ Denotes co-first authors; equal contributors

Abstract

Background: Ambient artificial intelligence (AI) scribe technologies have shown early promise in alleviating documentation burden and physician burnout. However, to our knowledge, these tools have not been rigorously evaluated in a randomized controlled trial (RCT).

Methods: This is a three-arm pragmatic RCT of 238 outpatient physicians at a large academic health system, randomized 1:1:1 to one of two ambient AI scribe tools or a usual-care control group. The two-month study will compare the effects of each tool. We will use covariate-constrained randomization to balance the arms in terms of physician baseline time in notes, survey-measured level of burnout, and clinic days per week.

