Eligible participants for this study included ambulatory care physicians across multiple specialties within the UCLA Health system who held at least one half-day of clinic per week. Trainee providers (e.g., residents, medical students) and allied healthcare professionals (e.g., RNs, PAs) were excluded, along with attendings who work exclusively with trainees and provide no direct patient care. Only English-language encounters are included due to a lack of internal validation for translation capabilities in the vendor technologies. Physicians who typically use a human scribe agreed to forego this assistance while assigned to an intervention or control group. Due to the technical requirements of one vendor, all providers are required to use an iOS portable device.

Participants were recruited based on specific department leadership suggestions and non-specific department-wide emails, resulting in 331 provider invitations. Of these, only 238 met the study criteria. Reasons for exclusion included ineligibility (e.g., did not meet inclusion criteria; $n = 7$), refusal to participate ($n = 21$), status as a key decision-maker (to prevent potential conflicts of interest in outcome assessment; $n = 20$), or failure to

complete the baseline survey (n = 43). Participants who met eligibility requirements and agreed to participate were required to complete a pre-implementation survey prior to randomization.

Study Design and Randomization

Eligible physicians (n = 238) were randomized into one of three groups: either of the two ambient AI scribe technologies (Vendor A or Vendor B) or a control group with no scribe (Figure 1). Randomization followed a 1:1:1 allocation over a two-month period and analysis will follow an intention-to-treat approach. Since both vendor tools are being rolled out from November 4, 2024 to January 3, 2025, secular trends, seasonal variations, and clinic holiday closures are accounted for by comparing effects of Vendor A and Vendor B with results from a contemporaneous control group.

Covariate-constrained randomization was conducted by the trial statistician to balance participants' baseline geometric mean time in notes per note collected over the prior year, as well as burnout scores and clinic days per week obtained from survey data.

Intervention and Implementation

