The primary analysis will evaluate the impact of each intervention arm (Vendor A and Vendor B) compared to the control group. Specifically, the two primary comparisons are (1) Vendor A vs. Control and (2) Vendor B vs. Control. The primary outcome, the change in second month's (log-transformed) time in notes per note from the provider's prior six-month baseline, will be analyzed using a linear mixed-effects model. This model will include a study arm effect, a period effect (second vs. first month), and their interaction. Random physician effects will account for multiple timepoints per provider, and linear contrasts will evaluate differences between arms at the second month timepoint. We are

studying the period effect under the assumption that first month represents a learning phase and may not accurately reflect potential efficiency gains, while second month reflects proficiency with the tool. A two-sided 0.025 significance level (2-fold Bonferroni correction) will be used to account for multiple testing in the primary hypothesis tests.

Secondary outcomes will include measures such as burnout scores, task load, and professional fulfillment. These outcomes will be analyzed using similar statistical approaches, including comparisons of Vendor A and Vendor B to the control group, as well as an exploration of the relative impacts of Vendor A and Vendor B.

Our economic evaluations will entail a cost consequence analysis and a budget impact analysis.(24, 25) The cost-consequence analysis will separately present costs and outcomes associated with each intervention arm compared to the control arm. This analysis will show incremental costs as well as incremental benefits of each ambient AI scribe tool compared to the control group. The budget impact analysis will estimate the financial impact, from the perspective of the health system, of varying levels of implementation of each ambient AI scribe tool and project any potential gains in revenues through improvement in physician productivity and documentation efficiency.(24)

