include multiple vendors arms and a control arm. Results from this study will quantify how ambient AI scribes improve EHR documentation efficiency, affect burnout, and change physician engagement within a short intervention period. Additionally, this study evaluates physician-reported effects on note accuracy, patient safety, equity, and other unintended consequences, such as hallucinations or errors in text generation, addressing recognized limitations of LLM-based technologies.(26, 27) Similarly, understanding the economic impact of these tools, including costs related to physician adaptation and workflow changes, is essential to determine their value in real-world implementation.(18)

There are several limitations to this study. The relatively short duration of the intervention may not adequately capture the long-term effects of ambient AI scribes. Participants may require additional time to adapt to the ambient scribe technology, potentially delaying full proficiency. Since clinic schedules range from half-day to full-day sessions, the time needed for integration is likely to vary across participants. To address this variability, randomization was stratified by clinic schedules to ensure balanced adaptation periods among groups. Another potential limitation is that participation was voluntary, introducing the possibility of selection bias, as the findings may not fully generalize to all physicians. Furthermore, this study was conducted within a single academic health system using a specific EHR platform, which may limit the applicability of the results to other healthcare settings or systems.

This protocol does not evaluate the impact of ambient AI scribes on patient experience, satisfaction, or trust. While early studies suggest generally positive patient experiences with ambient AI scribes, existing studies have been limited by insufficient

power to draw definitive conclusions.(14, 15) Future research should explore not only patient satisfaction but also trust and perceptions of AI use in clinical settings, as these factors are crucial to widespread adoption. Looking ahead, we do hope to answer some if not all these questions in a larger roll out of the ambient AI scribe across the entire UCLA Health System.

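### The primary model omits the three variables used to constrain the randomization; adjusting for them is a low-cost gain in precision of unknown, possibly small, size

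*Combined protocol and SAP*

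**What the plan says.** The Abstract says that the allocation was meant to "balance the arms in terms of physician baseline time in notes, survey-measured level of burnout, and clinic days per week". Study Design and Randomization repeats this ("Covariate-constrained randomization was conducted by the trial statistician to balance") and specifies the time variable as the "baseline geometric mean time in notes per note collected over the prior year".

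Statistical Analysis defines the primary outcome as "the change in second month's (log-transformed) time in notes per note from the provider's prior six-month baseline" and lists the terms of the linear mixed model: "This model will include a study arm effect, a period effect (second vs. first month), and their interaction". It adds: "Random physician effects will account for multiple timepoints per provider". None of the constraining variables is named as a covariate in this model, here or elsewhere. Clinic days per week returns only as an effect modifier in the secondary subgroup analyses. Secondary outcomes are to be analysed by similar approaches.

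Sample Size rests on a two-sample t-test at two-sided 0.025, with 79 per arm, 0.50 SD and a log-scale SD of change of about 0.31. It calls this a conservative simplification of the mixed model.

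The Discussion describes the allocation differently: "randomization was stratified by clinic schedules to ensure balanced adaptation periods among groups".

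**The concern.** Constrained randomization discards allocations in which the arms differ on the chosen variables. If those variables predict the outcome, the arm difference varies less from one possible allocation to the next than it would under simple randomization. A model that leaves them out still counts their contribution as residual noise. Its standard error is then larger than the true sampling variation, its test is conservative, and it has less power than an adjusted model on the same data.

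Using a change score does not fully remove the issue. Subtraction forces the slope of follow-up on baseline to be 1. If the true slope differs from 1, the change still depends on baseline. The random physician effect does not help, because it absorbs between-physician variance without explaining it.

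What is at stake is precision. The sample could not easily grow, since Sample Size cites the exclusion criteria and a contractual cap of 100 concurrent users per tool. Covariates already in hand are therefore a natural place to look for it.

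**Working it through.** **Inputs from the documents.** 79 per arm (Figure 1 gives 80/79/79); effect 0.50 SD; two-sided alpha 0.025 per comparison; SD of log change 0.31.

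**Input not in the documents.** R2, the share of the variance of the log change explained by the three variables. It is an assumption throughout, shown from 0 upward.

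**Step 1: the plan's own figure.** A two-sample t-test (noncentral t) with 79 per arm, d = 0.50 and alpha 0.025 has power 80.9%, and 80% power needs 78 per arm. The stated 80% reproduces. It already uses the unadjusted SD of change, so leaving out the covariates does not take power below it.

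**Step 2: effect of adjustment.** The residual SD is multiplied by sqrt(1 − R2), so adjusted power is the t-test power at d = 0.50 / sqrt(1 − R2). For the unadjusted model under near-perfect balance, the limiting type I error is 2 × [1 − Φ(2.241 / sqrt(1 − R2))]. The unadjusted standard error is 0.31 × sqrt(2/79) = 0.049.

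| Assumed R2 | Adjusted / unadjusted SE | Adjusted power | Limiting type I error, unadjusted |
|---|---|---|---|
| 0 | 1.000 | 80.9% | 0.025 |
| 0.02 | 0.990 | 81.8% | 0.024 |
| 0.05 | 0.975 | 83.1% | 0.021 |
| 0.10 | 0.949 | 85.2% | 0.018 |
| 0.20 | 0.894 | 89.3% | 0.012 |

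The last column is a limit, because a real constrained scheme balances less than perfectly.

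**Step 3: simulation check.** 238 physicians, three equally predictive covariates, allocation drawn from the best 10% of 60 candidates, 4,000 runs per setting, one timepoint. The Monte Carlo error on a type I error of 0.025 is about sqrt(0.025 × 0.975 / 4000) = 0.0025.

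- R2 = 0: type I error 0.023 unadjusted and 0.023 adjusted; power 81.6% and 81.6%.
- R2 = 0.10: 0.023 and 0.027; power 80.9% and 84.3%.
- R2 = 0.20: 0.013 and 0.023; power 83.1% and 89.4%.

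The power gain appears as expected. The conservatism is not detectable at R2 = 0.10 under this scheme and is clear at 0.20.

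**Step 4: what R2 might be for baseline time in notes.** If β is the slope of follow-up on baseline, then R2 = (β − 1)² × Var(baseline) / Var(change). Two illustrations show how far this depends on assumptions.

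- Equal baseline and follow-up SDs with correlation rho: β = rho, so R2 = (1 − rho)/2. At rho = 0.69 this is 0.155.
- A stable physician level (variance k times the monthly noise variance) plus independent monthly noise, with a six-month baseline and a one-month follow-up: β = k / (k + 1/6) and R2 = (1/36) / [(7/6)(k + 1/6)]. A correlation of 0.69 corresponds to k = 1.19, so β = 0.88 and R2 = 0.0278 / (1.1667 × 1.354) = 0.018. Adjusted power is then 81.7%.

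The same correlation gives an R2 of about 16% or about 2%, depending on how the two windows relate.

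**The case against.** The strongest reply is that little is lost. The outcome is each physician's own change, so baseline is not ignored. The baseline averages six months (a full year for the constraining variable) and the follow-up is a single month. An average over more months normally carries less noise, which moves the slope towards 1 and the change score towards the efficiency of an adjusted analysis. In the stable-level model above, R2 is about 2%. Nothing in the documents shows that burnout score or clinic days predict the log change. Any error is conservative, and the promised power is met without adjustment. This stands, and it limits the size of the point. It is itself an assumption, though: persistent drift in a physician's documentation time would raise R2.

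A reader might infer more: that the planned standard errors are wrong, that the real type I error is well below 0.025, or that the trial is underpowered. The documents support none of these. The first two require covariates that predict the change, and no R2 or correlation is given. The third is contradicted by the reproduced 80.9%. Nor can a gain be read from the familiar variance ratio (1 + rho)/2, which assumes equal SDs and so does not fit windows of unequal length.

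It is also fair to object that changing a primary model after follow-up has ended is not free of risk. That stands and shapes the fix.

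**Conclusion.** The omission is real: three variables constrained the allocation and none is a covariate in the primary model. The consequence is forgone precision. It does not bias the estimate or inflate false positives. Against the 80.9% unadjusted t-test figure, the gain in power is nil at R2 = 0, about 1 point at 0.02, 2 at 0.05, 4 at 0.10 and 8 at 0.20. Against an unadjusted analysis of the constrained design it can be smaller, since that analysis also gains some power from balance: 6 points in the simulation at R2 = 0.20. The low end of the range is plausible. These figures assume 79 per arm, an effect of 0.50 SD and a single-timepoint comparison in place of the full mixed model.

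This is a worthwhile improvement and not a condition for a valid primary analysis. The Discussion's reference to stratification is a minor wording conflict that leaves the conclusion unchanged.

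**What to change.** In Statistical Analysis, add to the primary model, as fixed effects, centred baseline log time in notes per note with its interaction with period, baseline burnout score, and clinic days per week. For secondary outcomes use the same set plus the outcome's own baseline where one was collected. If the authors prefer the unadjusted model, they should say so and give the reason.

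State which baseline window supplies the covariate: Study Design and Randomization uses the prior year, while the primary outcome uses six months.

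Date the change. Trial Status says the trial period ended on January 3, 2025, and the document is dated January 28, 2025. State whether outcomes by arm had been seen when the change was made. If they had, keep the planned model as primary and report the adjusted model as a sensitivity analysis.

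Reconcile the Discussion's stratification wording with the constrained scheme in the Abstract and in Study Design and Randomization.

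The cost is a few sentences, a documented amendment and four fixed-effect parameters among 238 physicians. The covariates should be complete, because they were needed to randomize and the baseline survey was required beforehand.

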The RCT encompasses an 8-week period from November 4, 2024 to January 3, 2025. Physicians using ambient AI scribe tools will continue their usual clinical documentation processes, supported by the scribe software, which integrates with the EHR and automatically adds the generated text to the note. Training for each product was conducted 1–2 weeks prior to the intervention rollout and was standardized in terms of the time

allotted for each vendor and the format of internally generated support material. This included tipsheets, a recorded webinar, and two 1-hour-long virtual sessions for each vendor to demo the software functionality and workflow. Participants were free to discontinue their assigned intervention at any time. Reasons for discontinuation will be tracked and documented, and all participants will be analyzed on an intention-to-treat basis. To ensure participants adhered to the intervention protocols, comprehensive technical support was provided throughout the study. This included direct post-implementation support (dedicated communication channels, email listservs, and vendor contact), and regular check-ins by the UCLA IT team to help resolve any technical issues.

In compliance with California state law, all physicians must inform patients about the audio recording and obtain their verbal consent. Vendors do not retain any patient data, and recordings are not stored after transcription, following standard data protection and privacy protocols. Data from Epic System's Signal platform were collected starting six months before the 'go-live' date to establish baseline physician characteristics, like time spent writing a note, and for use in future outcomes analyses. At the end of the 2-month intervention period, participants will complete a post-implementation survey, which includes original survey questions and additional items to capture subjective impressions of each tool. Participant dropout is tracked throughout the study period, with reasons for discontinuation documented.

Study Outcomes

Primary Outcome

The primary outcome measure is the change in the time in notes per note in the second month of the trial from six months prior. The second month of the intervention was chosen to allow providers to familiarize themselves with the tools and workflow. This change will be computed on the natural log scale.

Secondary Outcomes

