We will perform pre-specified secondary subgroup analyses to investigate heterogeneous treatment effects by introducing interactions between primary model terms and potential effect modifiers. Specifically, these analyses will evaluate whether weekly clinic days, provider sex, and the proportion of visits from new vs. established patients moderate the intervention effects. These analyses will be conducted to meet out hypothesized differences in effects due to higher baseline burnout rates in women, an

246 anticipated bigger dose response in physicians with more visits per week, and higher
247 utilization for new patients where previous note text cannot be copied forward.

249 *Sample Size*

250 The sample size for this study is constrained by exclusion criteria and a contractual
251 limitation allowing at most 100 concurrent users of any given tool. A sample size of at least
252 79 providers per condition will provide 80% power to detect effect sizes as small as 0.50
253 standard deviations, assuming a two-sample t-test and a two-sided 0.025 significance
254 level. This is a conservative simplification of the planned linear mixed-effects regression
255 analysis.

256 Using pre-study data from a comparable timeframe, the estimated log-scale
257 standard deviation of change for the time in notes per note metric is approximately 0.31.
258 This design will be powered to detect a 15.5% relative improvement in the primary
259 outcome. Given a baseline-year geometric mean time in notes per note of approximately
260 4m 43s, this corresponds to an absolute difference of roughly 44 seconds. This effect size
261 falls within the range of those seen in the literature(17).

263 **Discussion**

264 Our study aims to evaluate the impact of ambient AI scribes on EHR utilization,
265 physician burnout, and billing capture in the ambulatory setting through a three-arm RCT
266 over a 2-month period. The study is the largest RCT of ambient AI scribes to date and first to

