 370 were excluded due to ineligibility, declining participation, incomplete surveys, or decision-
 371 making roles. The remaining 238 participants were randomized into three arms: Vendor A (n
 372 = 80), Vendor B (n = 79), and Control (n = 79). The study spans a two-month intervention
 373 period, with follow-up and analysis monitoring dropout counts due to discontinued
 374 intervention or insufficient data availability

375

Study Period	Enrollment	Allocation	Study Period
Timepoint	-1 month	- month	2 months
	Oct 2024	Nov 4, 2024	Nov 4, 2024 – Jan 3, 2025
Enrollment			
Eligibility Screen	X		
Informed Consent	X		
Randomization		X	
Interventions			
Vendor A or B			X
Control (Arm C)			
Provider-based Assessments^Φ			
Time in Notes per note (primary) [†]		X	X
Pajama time			X
After-hours (7 PM– 7 AM)			X
Mini-Z 2.0 Burnout Score	X		X
Professional Fulfillment Index	X		X
NASA Task Load	X		X
Physician Satisfaction	X		X
Net Promoter Score			X
Appointment Turnover Time			X
Relative-Value Units (RVU) per clinic			X

^Φ Change from baseline

[†] The primary outcome for 'Time in Notes per Note' is the second month (Dec 3, 2024 – Jan 3, 2025), though data from the entire study period are analyzed to evaluate period effects.

Table 1 – SPIRIT-AI Schedule of enrollment, interventions, and assessments outlining key study activities, including eligibility screening, consent, randomization, interventions, and outcome assessments. Primary and secondary measures, such as time in notes per note, burnout scores, task load, and productivity metrics, are collected at specified intervals during the enrollment, allocation, and study periods (October–December 2024)

References

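### The plain Bonferroni rule for the two primary comparisons is valid, but Holm's procedure would give more power within the same 5% family-wise limit, mainly if both vendors work

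*Combined protocol and SAP*

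**What the plan says.** The Statistical Analysis section defines the primary family: "Specifically, the two primary comparisons are (1) Vendor A vs. Control and (2) Vendor B vs. Control". It then sets the rule: "A two-sided 0.025 significance level (2-fold Bonferroni correction) will be used to account for multiple testing in the primary hypothesis tests". Twice 0.025 implies a family-wise level of 0.05.

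The Sample Size section uses the same level. It says that at least "79 providers per condition will provide 80% power to detect effect sizes as small as 0.50", and the next line continues "standard deviations, assuming a two-sample t-test and a two-sided 0.025 significance".

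No step-down or other multiplicity procedure is mentioned, and no reason is given for choosing plain Bonferroni. No confidence intervals are specified for the primary contrasts. The Background section states the hypothesis that each of the two tools reduces time in notes.

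**The concern.** Under plain Bonferroni, the second comparison stays at 0.025 even after the first has been rejected. Holm's procedure tests the smaller p-value at 0.025 and, if that is rejected, tests the other at 0.05. Any result that Bonferroni declares significant is also significant under Holm, and some further results are too.

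The trial hypothesises that both tools work, and this is the setting in which the unused second step gives away most. Each vendor's result also feeds its own cost-consequence and budget impact analysis, so a missed effect for one vendor could affect the business decision that the trial is meant to inform. The sample can no longer be enlarged, because recruitment and follow-up are over (Trial Status section).

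**Working it through.** **Inputs.** Two-sided 0.025 per comparison and two comparisons with one shared control (Statistical Analysis). Effect d = 0.50 SD, 79 per arm, two-sample t-test (Sample Size). With the stated log-scale SD of 0.31, 0.50 SD is 0.50 × 0.31 = 0.155 log units. Randomised numbers are 80, 79 and 79 (Figure 1 legend). The documents give no dropout rate or inflation, so dropout is taken as zero (assumption). Equal SDs are also assumed, and the plan's own t-test simplification stands in for the mixed model.

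**Step 1: reproduce the plan's figure.**
- Normal approximation: n = 2(z₀.₉₈₇₅ + z₀.₈₀)²/d² = 2(2.2414 + 0.8416)²/0.25 = 76.04, so 77 per arm. The t-test solution is 77.3, so 78 per arm.
- Power at 79 per arm: Φ(0.50 × √(79/2) − 2.2414) = Φ(3.1425 − 2.2414) = Φ(0.901) = 81.6%. By the noncentral t it is 80.9%.

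The stated 80% is reproduced.

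**Step 2: does Holm keep the 5% limit?**
- If both nulls are true, a false rejection requires the smaller p-value to be at most 0.025. Its probability is at most 0.025 + 0.025 = 0.05.
- If one null is true, it can be rejected only if its own p-value is at most 0.05. Its probability is at most 0.05.

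Neither step uses the correlation between the tests, so the shared control adds no assumption.

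**Step 3: where the gain comes from.** For vendor A,

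P(Holm rejects A) = P(p_A ≤ 0.025) + P(0.025 < p_A ≤ 0.05 and p_B ≤ 0.025).

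The second term is the whole gain. It cannot take per-vendor power above that of a test at 0.05, which is 87.8% at 79 per arm (t-test). The event that at least one comparison is rejected is the same under both rules.

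**Step 4: simulation.** 1,000,000 trials per scenario, 80/79/79, pairwise t-tests against the shared control (correlation about 0.5). Entries are percent rejected, Bonferroni → Holm.

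| True effects A, B (SD) | A | B | Both | At least one |
|---|---|---|---|---|
| 0.50, 0.50 | 81.2 → 85.7 | 80.9 → 85.5 | 70.2 → 79.3 | 92.0 → 92.0 |
| 0.40, 0.40 | 60.3 → 65.8 | 59.9 → 65.5 | 44.1 → 55.2 | 76.1 → 76.1 |
| 0.50, 0.25 | 81.2 → 81.8 | 24.8 → 33.6 | 23.7 → 33.1 | 82.3 → 82.3 |
| 0.50, 0 | 81.2 → 81.3 | 2.5 → 4.3 | 1.7 → 3.6 | 82.0 → 82.0 |
| 5, 0 (limiting case) | 100 → 100 | 2.5 → 5.0 | 2.5 → 5.0 | 100 → 100 |
| 0, 0 | 2.5 → 2.7 | 2.5 → 2.7 | 0.35 → 0.76 | 4.65 → 4.65 |

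Using the pooled three-arm variance (235 df) changes these figures by less than half a point. For example, power to show both at 0.50 SD goes from 70.6% to 79.5%.

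**Step 5: consistency with intervals.** Holm adds a rejection only when that p-value lies between 0.025 and 0.05, which is exactly when the 97.5% interval includes zero. With both effects at 0.50 SD this happens in 79.3 − 70.2 = 9.1% of trials, which is the entire gain in showing both.

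**The case against.** The strongest reply is that nothing here is wrong. The rule is prespecified and valid, it agrees with the sample size calculation, and the trial meets its own power target. That stands. A reader might infer that the trial is underpowered or its error control faulty, but Step 1 contradicts the first reading and the Bonferroni inequality the second.

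A reader might also infer that Holm costs nothing. The documents do not support that, for three reasons.
- Bonferroni tests and 97.5% intervals always agree. Holm has no equally simple matching intervals, and each rejection it adds conflicts with the Bonferroni interval.
- When only one vendor works, the other's false-positive rate rises, though it stays within the 5% family level.
- The intervention ended on January 3, 2025, the registration is dated January 27 and the document January 28. Moving to a more liberal rule after follow-up in a retrospectively registered trial carries a credibility cost. The documents do not say whether anyone had seen outcomes by arm.

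A third inference would be that the contract limit on users is what fixes the sample. The limit is 100 concurrent users per tool, and the arms have 80 and 79. It was not reached, and it does not apply to the control arm.

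Finally, a fixed threshold gives each vendor the same bar whatever its competitor's result, whereas under Holm one vendor's verdict can depend on the other's p-value. That is a defensible reason to prefer Bonferroni, although the documents do not give it.

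**Conclusion.** This is a missed efficiency and an optional improvement. It is not an error. Relative to the plan's rule, Holm never rejects less and stays within the same 5% family-wise limit.

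The size of the gain depends on the truth. At the design effect for both vendors it is about 4.6 points per vendor and about 9 points for showing both. It is about 0.2 points for the effective vendor if the other does nothing, and zero for showing at least one. It would therefore overstate the case to say that power rises for both comparisons whatever the true effects. The figures assume no dropout, equal SDs and the plan's t-test simplification.

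The plan says only that "Participant dropout is tracked throughout the study period, with reasons for discontinuation documented", and 79 per arm is one above the 78 that Bonferroni needs. If both effects are 0.50 SD, Holm reaches 80% per vendor with about 69 per arm. That cushion disappears if only one vendor works, when about 77 to 78 per arm are needed.

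**What to change.** If no outcome data by arm have been seen, replace the Bonferroni sentence in the Statistical Analysis section with:

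*The two primary comparisons are tested by Holm's procedure at family-wise two-sided 0.05 (smaller p-value at 0.025; if rejected, the other at 0.05).*

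Date the change before the analysis, and state that arm-level outcomes had not been seen. Apply it to the p-values of the two second-month contrasts from the planned mixed model; the model itself does not change. Report Holm-adjusted p-values: twice the smaller p-value, and for the other the larger of that value and its own p-value, each capped at 1 and compared with 0.05. If 97.5% intervals are shown, label them as Bonferroni intervals and say that one of them may include zero although Holm rejects. The 80% power statement at 0.025 can stay as a lower bound.

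If outcome data by arm have been seen, keep Bonferroni as the primary rule.

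The cost is one sentence, a dated note and the interval caveat. No new data, participants or modelling are needed.
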